2. Objectives/Endpoints

The primary objective of this Phase I/II study is to determine the maximum tolerated dose (MTD) of oral curcumin in patients who have chemotherapy-induced mucositis. The secondary objectives of this study are to determine whether oral curcumin:

- Decreases an objective measurement of oral mucositis
- Decreases the pain associated with oral mucositis
- Decreases the duration of mucositis
- Has an acceptable safety profile.

3. Study Design

This is a phase I/II study involving 2 parts: a dose escalation part and an expansion at the maximum tolerated dose.

In the first part, there will be 3 subjects at each dose level of curcumin (see table below). The doses will be taken 3 times each day for 14 days. Each dose will be taken as a mouth rinse containing curcumin and water, 3 times each day for 14 days. The mouth rinse will be used for 30 seconds and then swallowed. Subjects will be evaluated for dose-limiting toxicity (DLT, defined in section 6.1). The maximum tolerated dose (MTD, defined in section 2) will be determined. Subjects may participate in the study at a higher dose level, after they have completed the study at the current dose level and if they are eligible.

# Subjects	Curcumin/dose (gram)	Curcumin/day (gram)
3	0.33	1
3	1.0	3
3	2.0	6
3	3.0	9

In the second part of the study, there will be 23 subjects enrolled to an experimental (curcumin) arm and 23 subjects enrolled to a control (standard of care) arm. Subjects will be randomized to take a mouth rinse with or without the MTD of curcumin, 3 times each day for 14 days. The rinses will be swallowed. Subjects will be evaluated for response and toxicity. Subjects in the first part of the study may participate in the second part of the study, if they are eligible.

In both parts of the study, if the mucositis score \leq Grade 2 but is unresolved after 14 days of taking the study mouth rinse (curcumin or control), then the subject will

continue to receive the study mouth rinse until the mucositis is resolved (Grade 0).

This study will involve 12 subjects in the first part, plus an additional 3 subjects if a dose-limiting toxicity occurs (see section 2) and 46 subjects in the second part for a total of 61 subjects. This study is expected to take 2 years to complete enrollment, treatment and follow-up (6 months for the first part and 18 months for the second part).

4. Subject Selection

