5.6 Determination of MTD

The MTD will be determined as follows: If a DLT occurs in any one of the 3 patients at a specific dose level, an additional 3 patients must be treated at that dose level to achieve statistical validity of the MTD. If 2 of the 6 patients (17%) at a dose level develop a DLT, the previous dose level will be used as the MTD. If no DLT is observed, then the MTD will be the highest dose. To ensure safety of subjects at each dose level, all assessments will be completed at Visit 5 for subjects at a dose level before another subject is given study drug at the

subsequent dose level.

6. Expected Adverse Events

Toxicities will be graded by health care providers using the Common Terminology Criteria for Adverse Events (CTCAE) Version 4.0 weekly after initiation of study mouth rinse until mucositis is resolved (Grade 0) (see Provider Assessment in calendar, section 5.2). Toxicities will be assessed by subject self-evaluation during study mouth rinse administration between clinic visits (see Subject Assessment in calendar, section 5.2).

Very few studies have reported any severe or serious side effects from curcumin and most studies have involved oral administration of curcumin. No major toxicity has been found in studies where curcumin is used short-term. Increased bleeding may occur due to inhibition of platelet aggregation (very rare). Possible other side effects associated with curcumin include: vomiting, nausea, rash and GI distress. In a study of subjects with colon cancer, oral curcumin at doses ranging from 0.45 to 3.6 gram/day for 1 to 4 months was associated with nausea and diarrhea and caused an increase in serum alkaline phosphatase and lactate dehydrogenase[15]. In one study of patients with advanced pancreatic cancer, 5 of the 17 patients receiving oral curcumin (8 gram/day) in combination with gemcitabine reported intractable abdominal pain after a few days to 2 weeks of curcumin intake[16]. In a recent study of topical curcumin for mucositis in juveniles and children[14], there were no oral adverse events documented and no systemic adverse events that possibly could be related to the use of the curcumin mouthwash.

Patients will receive full supportive care as appropriate. The rationale for treatment, dosage and the date of treatment will be recorded in the medical record.

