6.1 Dose-limiting Toxicity

DLT resulting from any treatment component of the study will be defined in the list below. There will be no dose reductions in response to DLT.

- Any grade 2 or greater allergic response
- Any grade 3 or greater toxicity

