This study will involve 12 subjects in the first part, plus an additional 3 subjects if a dose-limiting toxicity occurs (see section 2). This sample size is similar to other phase I dose escalation studies and will result in a determination of maximum-tolerated dose. The first objective for the second part (n=46) is to determine whether curcumin decreases an objective measurement of oral mucositis. Mucositis assessment will be conducted by the provider using the WHO scale and CTCAE scale. The scales are continuous between 0 and 4. Analysis of variance will be used to compare the two groups of subjects (standard mouth rinse versus study mouth rinse) separately for each time period (baseline and each week after study mouth rinse initiation). In a one-way ANOVA study, sample sizes of 23, and 23 are obtained from the 2 groups whose means are to be compared. The total sample of 46 subjects achieves 91% power to detect differences among the means versus the alternative of equal means using an F test with a 0.05 significance level. The size of the variation in the means is represented by their standard deviation which is 0.50. The common standard deviation within a group is assumed to be 1.00.

9. Measurement of Effect

Differences between the two mouth rinse groups will be studied with the chi-square test for categorical factors and the analysis of variance F-test for continuous variables with a 0.05 significance level.

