9.6 Criteria to be Evaluable for Efficacy and Safety

A subject is evaluable for efficacy (reduction in mucositis) if at least 70% of the study mouth rinse doses were taken as documented on the daily log (Appendix A). Differences between groups in terms of response rate will be evaluated by ANOVA (section 8).

A subject is evaluable for safety (toxicity) if a minimum of one dose of the study mouth rinse was taken.

10. Correlative Studies (Laboratory Studies)

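### If no DLT occurs, section 5.6 declares 9 g/day the MTD on 0 of 3 subjects, although the data show only that no MTD was reached

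*Combined protocol and SAP*

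**What the plan says.** Sections 2 and 5.6 make determination of the MTD the primary objective and give the rule for it. Section 3 sets four levels of three subjects, ending at 9 g/day. Under section 5.6, one DLT among three subjects brings three more to that level, and two DLTs among six make the level below the MTD. For a clean escalation the rule is: "If no DLT is observed, then the MTD will be the highest dose". Section 8 states without condition that the first-part sample size "will result in a determination of maximum-tolerated dose".

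Section 3 refers to section 2 for the definition of the MTD, but section 2 lists only objectives. No section provides for an outcome in which the MTD is not reached, or for a recommended dose distinct from the MTD.

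Section 3 also allows re-entry: "Subjects may participate in the study at a higher dose level, after they have completed the study at the current dose level", provided they are eligible. Under section 6.2 a DLT removes a subject from the study.

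Toxicity is followed in the second part. Section 2 lists as a secondary objective whether curcumin "Has an acceptable safety profile", section 9.5 has toxicity graded weekly, and section 9.6 says "A subject is evaluable for safety (toxicity) if a minimum of one dose of the study mouth rinse was taken".

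**The concern.** An MTD is a statement about two things: the named dose is tolerated, and a higher dose is not. If no DLT is seen at any level, nothing has been learned about the second. What the trial has then is a highest dose tested, and the MTD, if there is one, has not been reached. Section 5.6 nevertheless requires the label, and section 8 promises it.

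The first half is thinly supported too, because a level with no DLT stops at three subjects. After a single DLT, section 5.6 asks for three more patients so that the MTD is statistically valid; on the clean branch it accepts three in all.

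At stake is the primary result. A report of 'MTD = 9 g/day' could be taken by later users as an established limit when the evidence is 0 of 3 at the top planned dose.

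**Working it through.** **Inputs.** Four levels of 3 subjects, top level 9 g/day (sections 3 and 5.5). Expansion by 3 only after a DLT, and step-back at 2 of 6 (section 5.6). The document prints 17% beside 2 of 6. Since 2/6 = 33% and 1/6 = 17%, I use 33%; that slip is a separate matter and nothing here depends on it.

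**The plan's own figures.** With no DLT, the first part has 4 × 3 = 12 subjects, as section 8 states. With 3 more and the second part, 12 + 3 + 46 = 61, as section 3 states. On the clean branch the top level therefore holds exactly 3 subjects.

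**What 0 of 3 excludes.** The exact upper limit for 0 events in n is 1 − α^(1/n).
- One-sided 95%: 1 − 0.05^(1/3) = 0.632, or 63%.
- Two-sided 95%: 1 − 0.025^(1/3) = 0.708, or 71%.

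Both lie well above 33%. These limits treat the three as unselected. If some had completed a lower level without a DLT, the limits would be optimistic for patients new to curcumin.

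**How easily a clean top level arises.** The chance of 0 of 3 at a true DLT rate p is (1 − p)³:

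| True DLT rate at 9 g/day | Chance of 0 of 3 |
|---|---|
| 1/6 | 58% |
| 20% | 51% |
| 33% | 30% |
| 50% | 12.5% |

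These apply once the top level has been reached.

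**How likely the whole branch is.** The documents give no DLT rates, so these are assumptions. With the same rate at all four levels, the chance of no DLT in 12 subjects is (1 − p)^12: 78% at 2%, 54% at 5% and 28% at 10%. With rising rates of 2%, 5%, 15% and 33%, it is (0.98 × 0.95 × 0.85 × 0.67)³ = 0.149, or 15%. The branch is likely if curcumin is as benign as section 6 suggests, and still possible if the top dose sits at the plan's own step-back rate.

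**What the second part could add.** With 23 curcumin subjects, 0 DLTs would give an exact two-sided 95% interval from 0 to 1 − 0.025^(1/23) = 0.148, or 15%. Five DLTs of 23 would give 7.5% to 43.7% (Clopper-Pearson). That is far more informative than 0 of 3, but no section says how it would qualify an MTD already declared.

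**The case against.** The strongest reply is that this is a matter of naming. The rule is stated openly in advance, so a reader with the DLT counts could decode the result. Taking the top planned dose forward after a clean escalation is common and can be defended. The 63% limit attaches to any 0-of-3 cohort, including a level reached by stepping back, and rewording does not shrink it.

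Much of this stands. Carrying 9 g/day into the second part is not challenged. But the name is the answer to the primary objective, so naming it wrongly matters. The step-back branch also differs: there a higher dose has been found not tolerated, so the label has a basis even if the lower level holds only three subjects.

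The re-entry point is a possibility, not a forecast. A returning subject must again be eligible, including the mucositis grade, and nothing indicates how often that would happen.

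A reader might infer that section 6 already shows 9 g/day to be too toxic, since "5 of the 17 patients receiving oral curcumin (8 gram/day) in combination with gemcitabine reported intractable abdominal pain". The documents do not support that. Those patients had advanced pancreatic cancer and received gemcitabine, no grade is given, and the same paragraph reports no major toxicity with short-term use. The figure is at most an illustration.

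A reader might also infer that toxicity goes unwatched in the second part. It does not: besides sections 9.5 and 9.6, section 6.2 removes subjects with a DLT, section 6.3 holds the trial for a Grade V toxicity, section 6.4 allows dose reduction, and section 12 has the Principal Investigator review toxicities weekly. Nor does "Any grade 3 or greater toxicity" by itself mean that background chemotherapy toxicity will inflate the DLT count. The lead-in to section 6.1 ties a DLT to a component of study treatment.

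**Conclusion.** The concern holds as a defect in how the primary result is declared. On the no-DLT branch, sections 5.6 and 8 require an MTD of 9 g/day to be reported when the data support only 0 DLTs in 3 subjects at the highest dose tested, compatible with DLT rates up to 63% one-sided (71% two-sided). It rests on the rule as written, on expansion occurring only after a DLT, and on there being no alternative outcome anywhere in the protocol. The limits assume three unselected, independent subjects.

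It does not show that 9 g/day is unsafe, that it exceeds the true MTD, or that a different dose should enter the second part. The trial can run as designed; the wording should be corrected before the result is reported.

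**What to change.** In sections 5.6 and 8, state that if no DLT is observed the result is 'MTD not reached; 9 g/day is the highest dose tested', and remove the unconditional promise of an MTD from section 8. Carry 9 g/day into the second part under that name.

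Report the number of DLTs at 9 g/day with the exact (Clopper-Pearson) 95% interval for the first part and, separately and descriptively, for the second-part curcumin arm. Showing the control arm alongside, giving counts with and without subjects who return from the first part (section 3 allows it: "Subjects in the first part of the study may participate in the second part of the study, if they are eligible"), or adding a pooled figure is optional.

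The cost is protocol wording and a short table from data already collected. No subjects, doses or tests change. The downside is that the trial may have to report that its primary objective ended without an MTD.

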6.1 Dose-limiting Toxicity

DLT resulting from any treatment component of the study will be defined in the list below. There will be no dose reductions in response to DLT.

- Any grade 2 or greater allergic response
- Any grade 3 or greater toxicity

6.2 Criteria for Subject Removal

A subject will be removed from the study for the following reasons:

- Dose limiting toxicity.
- No improvement in mucositis after 14 days of taking the study mouth rinse.
- Patient decision to withdraw consent or discontinue the study.
- Deemed by the physician to be the best medical interest of the patient.
- At the discretion of the investigator, patients who are non-compliant.

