6.3 Criteria for Study Discontinuation

If 2 patients develop a DLT at dose 1, then the trial will be closed due to unacceptable toxicity. If any patient has Grade V toxicity, then, the trial will be placed on immediate hold until the protocol investigators, the sponsor of the IND, the IRB and the FDA have been notified and a determination has been made as to the re-opening of this trial.

If < 5 of the first 10 subjects in the curcumin arm of the second part of the study have Grade 0 mucositis (CTAE version 4.0 and WHO Oral Toxicity Scale) at Visit 4, then the study will be discontinued due to lack of activity.

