9.5 Determination of toxicity profile

Toxicities will be graded by health care providers using the Common Terminology Criteria for Adverse Events (CTCAE) Version 4.0. A baseline evaluation will occur prior to study mouth rinse administration, and then weekly during study mouth rinse administration. Data will be recorded and entered into a database.

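### Section 6.2 takes subjects out of the study, not only off the rinse, for toxicity, physician decision or non-compliance, and the follow-up passages conflict on what is assessed afterwards

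*Combined protocol and SAP*

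**What the plan says.** Section 6.2 of the protocol has one list with one consequence: "A subject will be removed from the study for the following reasons". Besides withdrawal of consent and lack of improvement after 14 days, the list contains:

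- "Dose limiting toxicity", which Section 6.1 defines to include "Any grade 3 or greater toxicity";
- "Deemed by the physician to be the best medical interest of the patient";
- "At the discretion of the investigator, patients who are non-compliant".

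The list is not limited to Part 1. The protocol describes no early-termination visit and gives no rule for missing data.

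Other passages bear on follow-up:

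- Section 6 grades toxicity "weekly after initiation of study mouth rinse until mucositis is resolved (Grade 0".
- Section 9.1 has the provider assess mucositis in every week after the rinse is started.
- Section 9.5 says: "A baseline evaluation will occur prior to study mouth rinse administration, and then weekly during study mouth rinse administration".
- The Section 5.2 calendar marks the mucositis grade and adverse event collection at Visits 3 and 4 without condition. Most later items carry footnote a, which restricts them to subjects still on the rinse. A Final visit column is unconditional, but Section 5.1 never describes that visit.

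Section 6.3 closes the study for lack of activity "If < 5 of the first 10 subjects in the curcumin arm of the second part of the study have Grade 0 mucositis" at Visit 4.

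**The concern.** Withdrawal of consent has to end data collection. Toxicity, a physician's decision and poor adherence need only end the rinse. Section 6.2 treats them alike. A Part 2 subject removed for toxicity on day 4, or judged non-compliant at Visit 3, has no stated route to a Visit 4 grade, to the day 10 or 11 self-assessment, or to follow-up of the event.

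Such losses are unlikely to be random, because the reasons for removal are tolerability and adherence. The arms are visibly different: Section 5.3 describes a pharmacy-prepared liquid and Section 5.4 a powder mixed with water at home. No blinding is described, and two of the removal grounds are matters of judgement. The independent graders in Section 9.1 cannot help if the grading visit does not take place.

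At stake are the week-2 comparison, pain, healing time under Section 9.4 (a removed subject has no recorded Grade 0 day, and no censoring rule is given), the Section 6.3 count and the toxicity profile. Section 5.6 is also touched: it requires assessments through Visit 5 at one dose level before the next opens, while Section 6.2 removes the subject who had the toxicity.

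**Working it through.** **1. The passages side by side**

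| Place | After the rinse is stopped |
|---|---|
| Section 6 | toxicity weekly to Grade 0 mucositis; not tied to taking the rinse |
| Section 9.1 | mucositis weekly after initiation; not tied to taking the rinse |
| Section 9.5 | toxicity only while taking the rinse |
| Section 5.2, Visits 3 and 4 | grade and adverse events unconditional |
| Section 5.2, Week 4 onward | header runs until mucositis is resolved and there are no adverse events, but the entries carry footnote a |
| Section 5.2, Final visit | unconditional; timing and attendance undefined |
| Section 6.2 | subject is out of the study |

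These cannot all be followed for a removed subject, and none says which prevails.

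**2. The plan's own power figure**

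Section 8 gives 23 per arm, a standard deviation of the two means of 0.50, a within-group standard deviation of 1.00 and an F test at 0.05. With two equal groups each mean lies 0.50 from the grand mean, so the difference is 2 × 0.50 = 1.0 grade. The noncentrality is 1.0² / (1/23 + 1/23) = 11.5 on 1 and 44 degrees of freedom, which gives 91.2%. The stated 91% reproduces, and it assumes that all 46 subjects contribute.

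**3. Power if subjects are lost** (loss rates assumed; the documents give none)

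| Assessed, curcumin vs control | Power for 1.0 grade |
|---|---|
| 21 vs 21 | 88.5% |
| 20 vs 20 | 86.9% |
| 18 vs 18 | 83.0% |
| 16 vs 16 | 78.1% |
| 20 vs 23 | 89.1% |

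A few losses cost little power, so bias is the larger worry.

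**4. Bias in one arm's mean** (values assumed)

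Let m of 23 curcumin subjects be removed before Visit 4. Let their true Visit 4 mean grade be g, and let the others average 1.0. Then the all-randomised mean minus the observed mean is (m/23) × (g − 1.0).

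| m | g = 1 | g = 2 | g = 3 |
|---|---|---|---|
| 2 | 0 | 0.09 | 0.17 |
| 3 | 0 | 0.13 | 0.26 |
| 4 | 0 | 0.17 | 0.35 |

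For m = 3 and g = 3: (20 × 1.0 + 3 × 3.0)/23 = 29/23 = 1.26, against an observed 1.00. If g were 0, the same formula gives −0.13, so the sign can reverse. The bias in the between-arm difference is this quantity for curcumin minus the same quantity for control. Equal losses of equally affected subjects would cancel.

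**5. Overlap with the 70% rule in Section 9.6**

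Three doses on 14 days is 42, and 0.70 × 42 = 29.4. If the rule refers to planned doses, 30 are needed, reached at the end of day 10 when no dose is missed. Subjects who stop before that are outside the efficacy set even if they are graded at Visit 4. A subject removed on days 11 to 13 can be evaluable and yet have no Visit 4 grade.

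**6. The Section 6.3 count**

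Suppose 4 of 9 assessed curcumin subjects are at Grade 0 and the tenth was removed earlier. Read literally, the count is 4, below 5, and the study closes. Had the tenth been graded and found at Grade 0, the count would be 5 and the study would continue.

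**The case against.** The strongest reply is that later data may well be collected. The calendar marks Visits 3 and 4 without condition, Section 9.1 continues weekly, Section 6 grades toxicity to Grade 0, and there is a Final visit. Section 5.1.8 asks for the daily log at Visit 5 only from subjects still on the rinse, so it already expects some attendees who are off it. This stands: a reader might infer from Section 6.2 that removed subjects have no later data, and the documents do not prove that. What they show is a conflict, with nothing saying that a removed subject attends any of these visits. Nor does the point reach everyone who stops early. It concerns those removed under Section 6.2, and removal for non-compliance is discretionary.

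A reader might also infer that the toxicity behind a removal is never followed to its outcome. Section 6.2 is silent on this. The Week 4 column header points the other way, and Section 13.1 requires a complete report when the event is serious. No passage settles it for other events.

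It is tempting to say that the curcumin mean would be flattered. That is possible but not established. Section 6.1 covers any treatment component and does not require attribution to curcumin, so control subjects can be removed too, and a toxicity need not coincide with severe mucositis. Section 6 cites 5 of 17 patients with intractable abdominal pain on 8 g/day with gemcitabine, within days to 2 weeks; the highest level here is 9 g/day. That makes early removals plausible but gives no rate.

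The Section 6.3 denominator is not ambiguous either: read literally, it stays at 10 and an ungraded subject does not count as Grade 0. The problem is only that the subject's true grade goes unused.

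Finally, Section 9.6 alone would exclude most early stoppers from the efficacy set. This stands, and it means that changing Section 6.2 is not enough by itself.

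**Conclusion.** The point holds as a conflict with a risk of bias. Section 6.2 as worded ends participation for reasons that need only end the rinse, and the protocol makes no provision for assessments afterwards. Followed literally, randomised subjects removed before Visit 4 may lack that grade, a later self-assessment or an adverse event outcome, and the losses can differ by arm.

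The size is not fixed by the documents. Under the assumptions of 3 of 23 removed in the curcumin arm only and the rest at mean grade 1.0, the error in that arm's mean runs from 0 to 0.26 grade as the removed subjects go from grade 1 to grade 3. The upper end is about a quarter of the 1.0-grade difference in Section 8. Control losses, or removed subjects with milder mucositis, would shrink or reverse it.

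This should be fixed, but it does not undermine the trial's main purpose: the primary objective is the maximum tolerated dose, and Part 2 efficacy is secondary. It is best settled before enrolment, because outcomes that were not collected cannot be recovered by a later choice of analysis set.

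**What to change.** Reconcile Sections 5.2, 6, 6.2, 9.1 and 9.5 as follows.

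- In Section 6.2, separate reasons that end the rinse (dose-limiting toxicity, physician decision, non-compliance) from withdrawal of consent to follow-up, which ends participation.
- State that subjects in both arms who are off the rinse but have not withdrawn that consent keep the scheduled Visits 3 to 5, with the provider's grade, the self-assessment and adverse event collection.
- State that the adverse event behind a removal is followed to its outcome, and align Section 9.5 and calendar footnote a with this.
- Define when the Final visit takes place and who attends.
- Use the actual Visit 4 grade of these subjects in the Section 6.3 count.
- Report the week-2 comparison in all randomised subjects with a Visit 4 grade, alongside the Section 9.6 set, since the 70% rule would otherwise still exclude most early stoppers.

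Who stops the rinse, and when, is unchanged. The cost is protocol wording and a few further visits for subjects who have stopped the rinse, with the burden that this puts on them and on the site.
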